1.1. General Introduction

The Stambil + is an electric stimulation unit used for the rehabilitation of those with paralysis. It is currently used at TIRR Memorial Hermann on nearly every patient with paralysis for the purposes of motor and sensory recovery. We are currently using the proposed TTNS protocol for research purposes (HSC-MS-15-0806) at TIRR for acute SCI during their inpatient rehabilitation admission. Based on the preliminary safety data, we believe we can develop this protocol for home use. The proposed protocol is using the device in a new way, to stimulate the nerves of the legs which is known to effect the bladder in a process described as “neuromodulation.”

The status quo as it pertains to the management of neurogenic bladder in SCI is anticholinergic medications to inhibit bladder activity, increase bladder capacity, and decrease detrusor pressures.⁴ However, management of neurogenic bladder requires further improvement, with an estimated 50% developing serious urologic complications.² Ongoing research regarding the neuromodulation of chronic neurogenic bladder is promising, demonstrating equal efficacy to current management without non-compliance and adverse medication side effects, with improved quality of life.⁵⁻⁸ Although neuro-modulation techniques are currently used for chronic neurogenic bladder, its use is limited to frequent clinic visits, imposing a barrier to a population known to have challenges accessing medical care. The proposed research is innovative, in our opinion, because it represents a substantive departure from the status quo by using transcutaneous tibial nerve stimulation in the home setting to improve bladder function. Rehabilitation horizons for neurogenic bladder management which have previously been unattainable through current efforts including the prevention of detrusor sphincter dyssynergia and related autonomic dysreflexia, maintenance of bladder capacity and compliance, and reduction in oral medication use with improved quality of life are also likely to become attainable.

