d. Rationale for Study Design

Based on our current inpatient experience, we believe this protocol can be performed safely at home by subjects and/or their caregivers if given detailed instructions. Subjects who perform intermittent catheterization are being selected because they more likely to have incontinence

than those with an indwelling catheter. If patients are interested, we will trial stimulation in clinic. We will exclude those who we cannot produce toe flexion with posterior tibial nerve stimulation. After 1 week of home stimulation, those that are on bladder medicine will discontinue the medication. There is no other harm from rapid discontinuation of bladder medication, except for incontinence. We expect that incontinence will be reduced from this first week of TTNS. The I-QOL questionnaire is administered at baseline, and at the end of 2 and 4 weeks to determine when best effects of TTNS are achieved.

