2.3. Secondary Objectives

Secondary Objective 1: I-QOL scores will improve and incontinence episodes will reduce after TTNS compared to baseline.

Secondary Objective 2: The frequency of catheterization and the volumes voided will improve with TTNS compared to baseline based on bladder diary.

Secondary Objective 3: Anticholinergic side effects will be reduced based on survey after TTNS protocol.

2.4. Potential Risks and Benefits:

a. End Points - Efficacy

Specific Aim 1: No efficacy requirement for the safety and feasibility studied in specific aim 1.

Specific Aim 2: We expect improved I-QOL scores compared to baseline. As a pilot trial, we have not powered the study for this measure. Results from this study will provide effect size to power a larger study.

b. End Points - Safety

Urinary Tract Infection (UTI) risk:

We expect the rates of morbidity to be the same between those who participate and those who do not. However, because UTI is directly related to the bladder, we will focus on the occurrence of UTI. Based on literature, the overall rate of UTI in SCI is about 2.5 episodes per patient per year. As a result, we expect to see 0.2 episodes per patient during the 4-week study period. Based on that, we construct the stopping rules to stop at 20% UTI rate using lower 90% exact Blyth-Still-Casella confidence bounds. If the number of patients with UTI exceed 3 in the first 5 patients, 4 in the first 10 patients, or 5 in the 14 patients, then patient accrual will be paused pending a review by a medical advisory board comprised of SCI experts.

Bladder medication discontinuation risk:

- Worsened incontinence

Electric Stimulation Risks:

Electric stimulation is commonly performed on the extremities of those with spinal cord injury at the study institution. There are few adverse reactions to electric stimulation. The common ones include:

- Pain with electric stimulation: in these cases, the intensity is reduced until it is comfortable.
- Skin irritation: it is common for redness to occur on the skin at the site of the surface electrode. This typically dissipates within an hour of removing the electrode. In some cases, the redness remains the next day. In these cases, they are likely sensitive to the adhesive used and a hypoallergenic skin electrode will be provided.

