3.3. Inclusion Criteria (table 1)

Table 1. Inclusion/ Exclusion Criteria

| Inclusion | Exclusion |
|------------------|---|
| 18-65 years old | Multiple medications for the bladder Cancer in the tibial nerve path and/or bladder. |

| | | |
|---|---|--|
| Neurologically stable SCI for ≥ 6 months | Other diagnoses to explain incontinence (ex: UTI, bladder stones, multiple sclerosis, etc.) | Inability to elicit toe/plantar flexion with electric stimulation during clinic visit. |
| Intermittent catheterization to empty bladder | 2+ pitting edema that does not resolve | Inability to understand directions |
| Stable bladder medications for ≥ 3 months | Known peripheral neuropathy or injury to the path of the tibial nerve | Non-English speaking |
| | Demand-type cardiac pacemaker or implanted defibrillator | |

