4. TRIAL SCHEDULE

Table 2. Timeline of protocol per subject

Weeks in Study Protocol

| Activities | 0 | W1 | W2 | W3 | W4 |
|--|---|---------|----|----|----|
| Clinic Enrolment: | | | | | |
| Eligibility screen | X | | | | |
| Informed Consent | X | | | | |
| Incontinence Questionnaire (I-QOL) | X | | | | |
| Side effect questionnaire | X | | | | |
| TTNS demonstration | X | | | | |
| Home | | | | | |
| Bladder diary | | □-----□ | | | |
| I-QOL | | | X | | X |
| TTNS | | □-----□ | | | |
| Discontinue bladder medication | | | X | | |
| Side effect questionnaire/ TTNS survey | | | | | X |

5. STUDY DESIGN (Table 2)

Anticipated number of patients to screen: 40

- Anticipated number of patient to enrol: 20
- Anticipated drop out or loss to follow-up: 4

Approximate time to complete study recruitment: 1 year

Expected duration of subject participation: 4 weeks

TTNS protocol: (please refer to protocol HSC-MS-15-0806) electrodes 2 inch by 2 inch will be placed according to anatomic landmarks, with the negative electrode behind the internal malleolus and the positive electrode 10cm superior to the negative electrode, verified with rhythmic flexion of the toes secondary to stimulation of the flexor digitorum and hallicus brevis. The intensity level will be set to the amperage immediately under the threshold for motor contraction. If there is not contraction seen, maximal tolerable intensity will be used. In addition, if the patient perceives pain, the intensity will be lowered until comfortable. Stimulation frequency of 10 Hz and pulse width of 200ms in continuous mode will be used.^{13, 14}

- Information gathered:
 - o Clinical demographics, morbidity, and Neurologic Exam findings from interview with subjects, exam, and EMR review.

- Bladder diary will include:
 - use of TTNS with amperage and presence of toe flexion, and pain score 0-10
 - log of catheterization, volumes
 - log of incontinence episodes
 - Description of other observed changes, including but not limited to: fatigue, vision changes, mental status, bowel program changes, and sexual function changes.
- Information will be tabulated on an Excel spreadsheet on my personal work desktop, password protected. Any paper data (bladder diary) will be de-identified and retained in a locked drawer in the locked office of the PI.

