8. TREATMENT

8.1. Rationale for Selection of Dose

Neuromodulation of the bladder is currently available with percutaneous TNS in the clinic setting, for a variety of patient populations. Stimulation frequency of 10 Hz and pulse width of 200ms in continuous mode will be used.^{13,14}

Neuromodulation of the bladder has been shown to be effective after 6-8 sessions, with sessions performed once weekly over 12 weeks or 3 times weekly. The 30 minute stimulation session is commonly used for bladder neuromodulation.^{23, 24}

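### In subjects on a bladder drug, every post-baseline I-QOL score falls after the planned drug stop, so the change measures replacing the drug with TTNS, not TTNS alone

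*Combined protocol and SAP*

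**What the plan says.** **I-QOL schedule.** Section 1.2 d gives the timing: "The I-QOL questionnaire is administered at baseline, and at the end of 2 and 4 weeks". The same sentence gives the purpose, which is to find the point at which TTNS works best. Table 2 in section 4 agrees on the timing, with marks at week 0, W2 and W4 only.

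**Drug stop.** Section 1.2 d: "After 1 week of home stimulation, those that are on bladder medicine will discontinue the medication". Table 2 marks the stop in the W2 column without a day: "Discontinue bladder medication | | | X".

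**State at baseline.** The inclusion criteria in section 3.3 require "Stable bladder medications for ≥ 3 months", so a medicated subject completes the baseline I-QOL on drug. The wording of section 1.2 d implies that some subjects take no bladder drug. The number in each group is not given.

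**Use of the result.** Hypothesis 2.1 (section 2.1) attributes the improvement in I-QOL to TTNS. Secondary Objective 1 (section 2.3) reads "I-QOL scores will improve and incontinence episodes will reduce after TTNS compared to baseline". Section 1.2 a says the I-QOL result will supply an effect size for powering later studies.

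**Analysis.** Section 11.2 compares results over time with baseline by paired or repeated-measures methods and adds an unspecified check of associations with bladder medication. There is no control arm (section 6.2: randomization not applicable).

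**The concern.** Between baseline and any later I-QOL, two things change in a medicated subject: TTNS is added and the drug is removed. The protocol expects these to pull in opposite directions, since section 2.4 lists worsened incontinence as the risk of stopping the drug. The one period in which only TTNS has changed is week 1, and no I-QOL is taken then.

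Three uses of the data are at stake:

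- attributing the I-QOL change to TTNS (Hypothesis 2.1);
- reading the week-2 and week-4 scores as the timing of the TTNS effect (section 1.2 d);
- passing an effect size to later trials (section 1.2 a).

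**Working it through.** The plan states no effect size, standard deviation or power for I-QOL, so there is no figure to reproduce. The check asks which effects the planned visits can identify.

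**1. Sequence for a medicated subject, taking the stop at the end of week 1 (section 1.2 d)**

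| I-QOL | TTNS | Drug | Time off drug |
|---|---|---|---|
| Baseline | no | yes | none |
| End of week 1 (not planned) | yes, 7 daily sessions | yes | none |
| End of week 2 | yes | no | 2 - 1 = 1 week |
| End of week 4 | yes | no | 4 - 1 = 3 weeks |

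If the Table 2 mark meant the end of week 2 instead, it would be unclear whether the week-2 I-QOL comes before or after the stop.

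**2. What the planned visits identify.** Let b be the baseline mean, T the TTNS effect and D the effect of losing the drug, each indexed by week. T also carries any uncontrolled time trend, in all subjects.

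- Y0 = b
- Y2 = b + T2 + D2
- Y4 = b + T4 + D4

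Then:

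- Y2 - Y0 = T2 + D2
- Y4 - Y0 = T4 + D4
- Y4 - Y2 = (T4 - T2) + (D4 - D2)

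Only the sums are estimable; a matrix-rank check confirms that T2, T4 and T4 - T2 are not. If D2 = D4 is assumed, T4 - T2 becomes estimable, but T2 and T4 still do not. The documents neither state nor contradict D2 = D4.

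**3. What a week-1 score adds.** With Y1 = b + T1, taken before the stop, Y1 - Y0 = T1 becomes estimable. T2 and T4 remain inseparable from D2 and D4.

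**4. Unmedicated subjects.** They have no D term, so Y2 - Y0 = T2 and Y4 - Y0 = T4. Borrowing these for medicated subjects requires assuming that the TTNS effect is the same in both groups.

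**5. Pooled effect size.** With a share p medicated, the pooled change is (1 - p)T + p(T + D) = T + pD. T and D below are assumed standardized values, because the documents give none.

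| Assumed T, D | p = 25% | p = 50% | p = 75% | p = 100% |
|---|---|---|---|---|
| 0.5, -0.5 | 0.375 | 0.25 | 0.125 | 0.00 |
| 0.8, -0.3 | 0.725 | 0.65 | 0.575 | 0.50 |

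For example, 0.5 + 0.25 × (-0.5) = 0.375. The same TTNS effect yields different pooled results depending only on the medication mix.

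**The case against.** **Replacement may be the intended question.** Section 1 presents home TTNS as a substitute for anticholinergic drugs, and Hypothesis 2.3 concerns the period after the drug is stopped. For that question, on-drug baseline against TTNS without drug is the right contrast. This stands, and the data remain useful for it. But section 1.2 d and Hypothesis 2.1 speak of the effect of TTNS itself, so the label does not match the contrast.

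**The plan has partial cover.** The bladder diary appears to run through week 1, so incontinence episodes are recorded on both sides of the stop, and section 11.2 mentions medication associations. However, Table 2 shows no diary before TTNS, the diary is not the I-QOL, and the section 11.2 clause does not commit to separate results by medication status.

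**I-QOL is secondary, exploratory and unpowered.** True, and it limits the weight of the point. A larger sample would not remove the mixing, though, and the effect size is a declared product of the study.

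**Stronger readings that the documents do not support:**

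- A reader might take the section 1.1 phrase "demonstrating equal efficacy to current management without non-compliance and adverse medication side effects" to mean that replacing the drug should leave I-QOL unchanged, so that an improvement-only objective would misread a successful TTNS as a failure. The same sentence goes on to claim better quality of life, so a directional objective is consistent with it. Section 11.2 also sets no I-QOL threshold.
- A reader might infer that the timing of the TTNS effect cannot be read at all. The week-2 to week-4 difference is confounded only if the drug-loss effect is still changing over that interval.
- A reader might expect a week-1 score to recover the full TTNS effect. Section 8.1 says "Neuromodulation of the bladder has been shown to be effective after 6-8 sessions", but it refers to sessions once or three times weekly in a paragraph on clinic-based percutaneous stimulation. Section 1.2 b gives 6-12 sessions. Seven daily home sessions may show only part of the effect.

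**Conclusion.** The point holds for medicated subjects. Their I-QOL change at weeks 2 and 4 is the net effect of replacing the drug with TTNS and cannot be attributed to TTNS alone. Their week-2 to week-4 trend may be confounded with time off drug. A pooled effect size depends on the unstated share on medication; in the assumed examples it ranges from 0.375 to 0.00, or from 0.725 to 0.50, as that share goes from 25% to 100%.

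This rests on the stop falling after week 1, as section 1.2 d says, and on the drug having some effect on I-QOL, whose size is not given. The point does not touch unmedicated subjects or the primary aims. It is a worthwhile low-cost improvement to Aim 2 and not a defect that undermines the study.

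**What to change.** - **Schedule.** Add an I-QOL before the drug stop, which under section 1.2 d means the end of week 1. Collect it at the weekly call already planned (sections 6 and 6.4) and mark it in Table 2.
- **Consistency.** Reconcile section 1.2 d (stop after one week) with Table 2 (stop under W2, no day given), so that the order of the I-QOL and the stop is explicit.
- **Analysis, section 11.2.** Report I-QOL change separately by baseline medication status, with the number in each group. For medicated subjects, label week 1 minus baseline as the one-week effect of adding TTNS with the drug unchanged, noting that it may understate the full effect. Label week 2 or week 4 minus baseline as the effect of replacing the drug with TTNS.
- **Timing.** In medicated subjects, do not read week 2 against week 4 as TTNS timing without stating the assumption of a constant drug-loss effect.

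The cost is one extra questionnaire per subject, with slight respondent burden, one mark in Table 2 and a few lines of text. Treatment is unchanged. The remedy is partial: the 4-week TTNS effect in medicated subjects remains inseparable from drug loss.

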2. HYPOTHESIS AND OBJECTIVES

2.1. Hypothesis

Specific Aim 1: **Determine the safety, feasibility, and compliance of a daily home TTNS protocol in chronic SCI provided by self or caregiver for 4 weeks.**

Hypothesis 1.1: TTNS at home is safe and feasible with high compliance.

Hypothesis 1.2: TTNS protocol will demonstrate overall satisfaction as a neurogenic bladder treatment option based on survey questionnaire.

Specific Aim 2. **Determine the efficacy of a 4 week TTNS protocol.**

Hypothesis 2.1: Incontinence quality of life scores and frequency of incontinence will improve with TTNS compared to their baseline.

Hypothesis 2.2: Frequency of catheterization and volumes voided will improve with TTNS compared to baseline measurements.

Hypothesis 2.3: Anticholinergic-related side effects will improve with TTNS after discontinuation of bladder medications

2.2. Primary Objectives

Primary Objective 1: Safety, feasibility, and compliance of TTNS at home.

Primary Objective 2: Overall satisfaction with TTNS based on survey.

2.3. Secondary Objectives

Secondary Objective 1: I-QOL scores will improve and incontinence episodes will reduce after TTNS compared to baseline.

Secondary Objective 2: The frequency of catheterization and the volumes voided will improve with TTNS compared to baseline based on bladder diary.

Secondary Objective 3: Anticholinergic side effects will be reduced based on survey after TTNS protocol.

2.4. Potential Risks and Benefits:

a. End Points - Efficacy

Specific Aim 1: No efficacy requirement for the safety and feasibility studied in specific aim 1.

Specific Aim 2: We expect improved I-QOL scores compared to baseline. As a pilot trial, we have not powered the study for this measure. Results from this study will provide effect size to power a larger study.

b. End Points - Safety

Urinary Tract Infection (UTI) risk:

We expect the rates of morbidity to be the same between those who participate and those who do not. However, because UTI is directly related to the bladder, we will focus on the occurrence of UTI. Based on literature, the overall rate of UTI in SCI is about 2.5 episodes per patient per year. As a result, we expect to see 0.2 episodes per patient during the 4-week study period. Based on that, we construct the stopping rules to stop at 20% UTI rate using lower 90% exact Blyth-Still-Casella confidence bounds. If the number of patients with UTI exceed 3 in the first 5 patients, 4 in the first 10 patients, or 5 in the 14 patients, then patient accrual will be paused pending a review by a medical advisory board comprised of SCI experts.

Bladder medication discontinuation risk:

- Worsened incontinence

Electric Stimulation Risks:

Electric stimulation is commonly performed on the extremities of those with spinal cord injury at the study institution. There are few adverse reactions to electric stimulation. The common ones include:

- Pain with electric stimulation: in these cases, the intensity is reduced until it is comfortable.
- Skin irritation: it is common for redness to occur on the skin at the site of the surface electrode. This typically dissipates within an hour of removing the electrode. In some cases, the redness remains the next day. In these cases, they are likely sensitive to the adhesive used and a hypoallergenic skin electrode will be provided.

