11.2. Statistical and Analytical Plans

This pilot study will serve as an earlier-phase developmental function that will enhance the probability of success in a larger subsequent randomization intervention trial.

In Aim 1, for safety, we hypothesize that there will be no unusual adverse events. However, because UTI is directly related to the bladder, we will focus on the occurrence of UTI. Based on literature, the overall rate of UTI in SCI is about 2.5 episodes per patient per year.¹⁸ As a result, we expect to see .2 episodes per patient during the 4-week study period. Based on that, we construct the stopping rules to stop at 20% UTI rate using lower 90% exact Blyth-Still-Casella confidence bounds. If the number of patients with UTI exceed 3 in the first 5 patients, 4 in the first 10 patients, or 5 in the 14 patients, then patient accrual will be paused pending a review by a medical advisory board comprised of SCI experts.

For feasibility and compliance, we will calculate descriptive statistics to determine the dropout rate and percent of adherence to the prescribed regimen as well as program satisfaction. If the dropout rate is less than 25%, and if subjects complete greater than 70% of daily TTNS use in the 4-week period, we will consider the study has high feasibility/adherence. If more than 80% of subjects report that they were satisfied with the program, then we will consider the study has high satisfaction.

In Aim 2, descriptive statistics will be provided for incontinence episodes, catheterization frequency, volumes voided, and anticholinergic-related side effects after the TTNS. The results along the time will be compared to baseline by paired t test, signed t test, or repeated measure methods when appropriate. Since this is an exploratory study and the efficacy of TTNS in this study will be further studied in future larger studies, Bonferroni correction will not be necessary. TTNS satisfaction will be based on the scores of a TTNS survey and descriptive analysis will be provided as well. We will also check the association between these changes from baseline, as well as bladder medication associations.

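### Incontinence episodes, catheterization frequency and volumes are to be compared with baseline, but the available text schedules no bladder diary before home TTNS and names no other baseline source

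*Combined protocol and SAP*

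**What the plan says.** Three diary outcomes are to be compared with baseline. Hypothesis 2.2 (sections 1.2 and 2.1) reads "Frequency of catheterization and volumes voided will improve with TTNS compared to baseline measurements". Hypothesis 2.1 makes the same kind of claim for frequency of incontinence. Secondary Objective 1 in section 2.3 says "I-QOL scores will improve and incontinence episodes will reduce after TTNS compared to baseline", and Secondary Objective 2 says "The frequency of catheterization and the volumes voided will improve with TTNS compared to baseline based on bladder diary", which names the diary as the source.

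For Aim 2, section 11.2 first says that "descriptive statistics will be provided for incontinence episodes, catheterization frequency, volumes voided, and anticholinergic-related side effects after the TTNS". The next sentence is "The results along the time will be compared to baseline by paired t test, signed t test, or repeated measure methods when appropriate". Three of the four outcomes listed just before that test sentence are diary outcomes. Baseline is not defined there.

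For I-QOL the timing is explicit. Section 1.2 d says "The I-QOL questionnaire is administered at baseline, and at the end of 2 and 4 weeks". The same section introduces a change of background treatment during the diary period: "After 1 week of home stimulation, those that are on bladder medicine will discontinue the medication". It adds: "There is no other harm from rapid discontinuation of bladder medication, except for incontinence".

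**The concern.** The trial has one arm, so each subject's own pre-treatment value is the only basis for estimating change. A paired test against baseline needs that value to be collected. If the diary starts together with stimulation, followed as written the plan yields only on-treatment data for these three outcomes.

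An analyst who still has to run the comparison would probably turn to week 1. That choice has two faults. Any benefit already present in week 1 is subtracted out. In medicated subjects, the later weeks also carry the effect of stopping medication, so they could appear to worsen on TTNS for a reason unrelated to TTNS. The pilot is meant to supply effect sizes for a larger trial, and pre-treatment diary data cannot be recovered once stimulation has begun.

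**Working it through.** The plan states no effect size, SD, alpha or power for these outcomes, so it has no figure to reproduce. The check sets the schedule, the data sources and the analysis text side by side.

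**1. Source and week-0 value of each Aim 2 outcome**

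| Outcome | Named source | Week-0 entry in Table 2 |
|---|---|---|
| I-QOL | Questionnaire | Yes (baseline also stated in 1.2 d) |
| Anticholinergic side effects | Questionnaire | Yes |
| Incontinence episodes | Diary (5, 5.1, 6) | No |
| Catheterization frequency | Diary (2.3, 5, 5.1) | No |
| Volumes | Diary (2.3, 5, 5.1, 6) | No |

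Two of five have a week-0 value; 5 − 2 = 3 do not. Section 5 also gathers data by interview, examination and medical-record review, but only for demographics, morbidity and neurologic findings. It does not list episode counts, catheterizations or volumes.

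**2. Is there diary time before stimulation?**

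- Table 2: the diary is a home activity, its week-0 cell is empty, and its row has the same form as the TTNS row.
- Section 5: expected participation is 4 weeks. Section 6.4: the TTNS goal is daily use for 4 weeks. 4 − 4 = 0 weeks left for a run-in.
- Section 6.4: home use is to begin promptly after the clinic trial and instruction. Some women wait for a pregnancy test result, but no diary is attached to that wait.
- Sections 6 and 6.4: weekly calls collect the diary data while monitoring progress on the protocol. No call before treatment is mentioned.

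On this reading, 0 of 4 scheduled diary weeks precede TTNS. In medicated subjects, 1 of 4 precedes the medication stop and 3 of 4 follow it.

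**3. What a week-1 reference would estimate**

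Assume effects add. Let T1 be the TTNS effect in week 1, T the TTNS effect in weeks 2–4, and M the effect of stopping medication (0 if unmedicated).

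- Week 1 minus pre-treatment = T1
- Weeks 2–4 minus pre-treatment = T + M
- Weeks 2–4 minus week 1 = (T − T1) + M

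With T1 = f × T, the last line becomes (1 − f) × T + M:

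| f (share of the effect already present in week 1) | Weeks 2–4 minus week 1 | Share of T kept |
|---|---|---|
| 0 | T + M | 100% |
| 0.5 | 0.5T + M | 50% |
| 1 | M | 0% |

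The documents give no value for f, but they point away from 0. Section 1.2 d expects incontinence to fall from the first week of TTNS. Section 8.1 cites an effect after 6–8 sessions, and daily use gives 1 × 7 = 7 sessions by the end of week 1. For incontinence episodes, T is negative if TTNS works. M is positive if stopping medication worsens incontinence, which is the risk listed in section 2.4. The contrast then shows apparent worsening whenever M exceeds (1 − f) × |T|, even though TTNS helped.

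**The case against.** The strongest objection is that this is a claim of absence and the likeliest places for a baseline diary were not available. The protocol lists appendices for the study schedule, the case report form and a sample voiding diary, any of which could contain one. This stands and limits the confidence of the finding. It also explains why the first remedy is to cite such a diary if it exists.

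Second, the bars in Table 2 are damaged. Read literally, both sit wholly in week 1, which contradicts 4 weeks of TTNS, so their exact edges prove little. That is fair, but the prose leads to the same place without the bars: participation and stimulation are equally long, the start is prompt, and no diary is mentioned before it.

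Third, these outcomes are secondary and unpowered in a pilot whose efficacy aim centres on I-QOL. That is true, and no primary objective, sample-size statement or stopping rule depends on them. It lowers the stakes but does not make a paired comparison possible without a reference value.

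Fourth, the mix of TTNS and medication stop is a separate matter that a baseline diary does not cure, and it affects I-QOL at weeks 2 and 4 as well. This also stands. I-QOL is unaffected only in that it has a baseline. The medication stop enters here because it makes week 1 unsuitable as a substitute.

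Finally, the range for f runs from nothing lost to everything lost, and the protocol never proposes a week-1 reference. The range shows how such a reference would behave; it does not estimate the bias.

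**Conclusion.** The concern holds, with moderate confidence. In the available text, three of the five Aim 2 outcomes have a planned comparison with baseline but no defined pre-treatment measurement, and none of the four diary weeks precedes TTNS. The size of any bias cannot be derived from the documents. Under the additive assumption, a week-1 reference retains (1 − f) of the weeks 2–4 TTNS effect and, in medicated subjects, adds all of M at every f.

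The conclusion rests on the prose more than on the table bars, and on the unseen appendices not containing a baseline diary. The primary objectives are untouched, and I-QOL and the side-effect questionnaire have their baselines. The descriptive reporting in section 11.2 can go ahead; only the comparison with baseline for the three diary outcomes is at stake. This should be fixed before enrolment.

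**What to change.** State when and how baseline is collected for the three diary outcomes, by one of three routes.

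1. **If an appendix already schedules a baseline diary:** cite it in Table 2 and in sections 6.4 and 11.2. This is a text change only.
2. **If not, and the comparison is wanted:** add to Table 2 and section 6.4 a short diary period between enrolment and the first home stimulation, on the existing form and under usual care. For example, 3 to 7 days; the length is for the sponsor to choose. Reconcile it with the prompt-start wording in section 6.4. In section 11.2, define baseline as each subject's daily mean over that period. Compare week 1 (medication unchanged) and weeks 2–4 with it separately, and describe results by bladder-medication status at entry without further tests. State that in medicated subjects the weeks 2–4 change is the combined result of TTNS and the medication stop. The same sentence is worth adding for I-QOL.
3. **If no pre-treatment diary is added:** remove the baseline comparison for these three outcomes from Hypotheses 2.1 and 2.2 (sections 1.2 and 2.1), section 2.3 and section 11.2, and report them descriptively by week. This is a text change only.

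Route 2 needs a protocol amendment, lengthens participation and moves the start of home stimulation by up to about a week. Whether that is acceptable is for the sponsor to decide. It does not separate TTNS from the medication stop in weeks 2–4; only the week-1 comparison is free of that change. The I-QOL schedule stays as planned under all three routes.
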